
Protocol Overview/Synopsis
	
After consent is obtained, eligibility will be assessed. Eligible participants will enter the Lead-in Period.
 
Lead-in Period:
 
The lead-in Period will last approximately 16 days, and may begin the same day the screening visit is completed. Participants will switch from their current Control-IQ system to the study pump (Control-IQ 1.5 technology) and study sensor, and will be trained by qualified study staff on the new study devices including use of Humalog (insulin lispro injection). Study participation will require use of the Control-IQ technology with at least 85% of active closed loop over ~16 days of the lead-in period. The lead-in period data collection may be repeated if this threshold is not met.
 
A study meal challenge and exercise challenge will be performed with Humalog during the lead in period. Those day and overnight periods will be analyzed separately.
 
Treatment Period:
 
Participants will return to clinic to undergo device training with Lyumjev in the study pump. Participants will then use the study pump and the investigational insulin for ~90 days during the study period. Participants will have a phone follow up visit at 1 week and 3 weeks, a clinic follow up visit at 6 weeks, a phone follow up visit at 9 weeks, and a final clinic visit at ~13 weeks.
 
Participants will use the t.slim X2 insulin pump with Control-IQ technology turned on with the investigational insulin. It is acceptable to use manual mode when there is a loss of CGM data.
 
Weekly phone/email/text contacts will be performed as part of the comprehensive plan to monitor for adverse events, to include infusion site reactions.
 
Each participant will perform 3 meal and 3 exercise challenges during Lyumjev use.
 
An assessment of adverse events, using open ended questions to capture hyperglycemic and hypoglycemic events, and their underlying cause and relationship to the study device, study insulin or other parts of the system (such as the infusion set), will occur at all visits/contacts.
 
Study Safety Plan:
 
Participants will be given a blood glucose and ketone meter to use throughout the study, and will be trained on their use by qualified staff. BGM readings will be performed in accordance with the study safety plan and per CGM manufacturer instructions. Ketone readings will be performed per the study safety plan.
 
Site investigators may adjust insulin delivery profile settings as needed throughout the study in accordance with their clinical practice.

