### 386 **3.1.3 Training on Management of Hyperglycemia**

387 The t:slim X2 with Control-IQ system will issue a predictive hyperglycemia alert (Control-IQ High Alert)  
388 when the system has increased insulin delivery, but detects a CGM value above 200 mg/dL and does not  
389 predict the value will decrease in the next 30 minutes. During the course of the study, participants will be  
390 permitted to change the CGM high glucose threshold alert setting on their device or mobile app, but will  
391 be instructed to choose a value no greater than 300 mg/dL.

392 If the participant receives a Control-IQ High Alert, a prompt appears on the user interface to check the  
393 site for occlusion and test blood glucose.

394 If a participant's CGM reading is >300 mg/dL for more than 60 minutes or is  $\geq$ 400 mg/dL at any point,  
395 the participant will be instructed to take the following steps:

- 396 • Perform a blood glucose meter check.
- 397 • If the blood glucose is >300 mg/dL, check for blood ketones with the study ketone meter.
- 398 • If the ketone level is  $\geq$  0.6 mmol/L (or  $\geq$  2.5 mmol/L at any time), take correction insulin, change  
399 insulin (pump) infusion site and contact study staff. Continue to monitor their glucose and blood  
400 ketone levels until they return to normoglycemia and ketones are < 0.6 mmol/l.
- 401 • If ketones are <0.6 mmol/l, they will be advised to continue to monitor their glucose until it  
402 returns to normoglycemia and to repeat the ketone measurement in 90 minutes if necessary
- 403 • If correction insulin is administered via insulin syringe, turn Control-IQ off for four hours and  
404 until glucose level has returned to <180 mg/dL.

405 **3.1.4 Participant Reporting of Infusion Set Insertion Reactions**

406 Participants will receive a weekly contact (phone, email and/or text message) to assess any issues related  
407 to their current infusion site.

408 Participants will be instructed to take a photo at time of removal of the first 2 infusion sets and  
409 subsequently photo at the time of removal only if there is redness on skin when the infusion set is  
410 removed. Additional photos may be needed if during a virtual visit, video is not available.

411 **3.1.5 Adjustments in Insulin Pump Settings**

412 Insulin and glucose data from the Lead-in Period will be reviewed and the site investigator may adjust  

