### 685 **6.2.3 Hypoglycemic Events**

686 Hypoglycemia not associated with an Adverse Device Effect or discontinuation of the study device or  
687 study drug is only reportable as an adverse event when one of the following criteria is met:

- 688 • a hypoglycemic event occurred meeting the following definition of severe hypoglycemia: the  
689 event required assistance of another person due to altered consciousness, and required another  
690 person to actively administer carbohydrate, glucagon, or other resuscitative actions. This means  
691 that the participant was impaired cognitively to the point that he/she was unable to treat  
692 himself/herself, was unable to verbalize his/ her needs, was incoherent, disoriented, and/or  
693 combative, or experienced seizure or loss of consciousness. These episodes may be associated  
694 with sufficient neuroglycopenia to induce seizure or loss of consciousness. If glucose  
695 measurements are not available during such an event, neurological recovery attributable to the  
696 restoration of glucose to normal is considered sufficient evidence that the event was induced by  
697 a low glucose concentration.
- 698 • evaluation or treatment was obtained at a health care provider facility for an acute event involving  
699 hypoglycemia, or the participant contacted the site and received guidance following the  
700 occurrence of an acute event involving hypoglycemia

701 When a severe hypoglycemia event occurs (as defined above), a Hypoglycemia Form should be  
702 completed in addition to the Adverse Event Form. Severe hypoglycemia events should be considered  
703 to be serious adverse events with respect to reporting requirements. When a severe hypoglycemia event  
704 occurs during use of a study device, it generally will be considered to be unrelated to the device (per  
705 section 6.2.6) if the device functioned as intended and there does not appear to be a flaw in how the  
706 device is intended to function.

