### 736 **6.2.6 Relationship of Adverse Event to Study Investigational Device**

737 The study investigator will assess the relationship of any adverse event to the study device or study drug.  
738 The Medical Monitor also will make this assessment, which may or may not agree with that of the study  
739 investigator. Reporting requirements will be based on the Medical Monitor's assessment.

740 To ensure consistency of adverse event causality assessments, investigators should apply the following  
741 general guidelines when determining whether an adverse event is related to a study device or study drug:

742 **Unrelated:** The AE is clearly not related to a study drug/device and a likely alternative etiology exists  
743 such as an underlying disease, environmental or toxic factors or other therapy.

744 **Unlikely Related:** The AE does not follow a reasonable temporal sequence during or after use of study  
745 drug/device and a more likely alternative etiology exists such as an underlying disease, environmental or  
746 toxic factors, or other therapy.

747 **Possibly Related:** The AE occurred in a reasonable time during or after use of study drug/device; but  
748 could be related to another factor such as an underlying disease, environmental or toxic factors, or other  
749 therapy; and there is a possible, though weak, scientific basis for establishing a causal association  
750 between the AE and the study drug/device.

751 **Probably Related:** The AE occurred in a reasonable time during or after use of study drug/device; is  
752 unlikely to be related to another factor such as an underlying disease, environmental or toxic factors, or  
753 other therapy; and there is a plausible, though not strong, scientific basis for establishing a causal  
754 association between the AE and the study drug/device.

755 **Definitely Related:** The AE occurred in a reasonable time during or after use of study drug/device;  
756 cannot be explained by another factor such as an underlying disease, environmental or toxic factors, or  
757 therapy; and there is a strong scientific basis for establishing a causal association between the AE and the  
758 study drug/device.

759 Events determined to be *Possibly Related*, *Probably Related*, or *Definitely Related* will be considered  
760 'Related' with respect to any required IRB and FDA reporting.

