### 825 **6.4 Timing of Event Reporting**

826 SAEs possibly related to a study device, study drug, or study participation and UADEs and SUSARs  
827 must be reported by the investigator to the Coordinating Center within 24 hours of the site becoming  
828 aware of the event. This can occur via phone or email, or by completion of the online serious adverse  
829 event form and device issue form if applicable. If the form is not initially completed, it should be  
830 completed as soon as possible after there is sufficient information to evaluate the event. All other  
831 reportable ADEs and other reportable AEs should be submitted by completion on the on line form  
832 within 7 days of the site becoming aware of the event.

833 The Coordinating Center will notify all participating investigators of any adverse event that is  
834 serious, related, and unexpected. Notification will be made within 10 working days after the  
835 Coordinating Center becomes aware of the event.

836 Each principal investigator is responsible for reporting serious study-related adverse events and abiding  
837 by any other reporting requirements specific to his/her Institutional Review Board or Ethics Committee.  
838 Where the JCHR IRB is the overseeing IRB, sites must report all serious, related adverse events within  
839 seven calendar days.

840 Upon receipt of a qualifying event, the Sponsor will investigate the event to determine if a UADE has  
841 occurred, and if indicated, report the results of the investigation to all overseeing IRBs, and the FDA  
842 within 10 working days of the Sponsor becoming aware of the UADE per 21CFR 812.46(b). A SUSAR  
843 must be reported within 7 calendar days if life threatening and 15 calendar days if not life threatening per  
844 21 CFR 312.32(c)(2). The Sponsor in conjunction with the Medical Monitor must determine if the UADE  
845 presents an unreasonable risk to participants. If so, the Sponsor must ensure that all investigations, or  
846 parts of investigations presenting that risk, are terminated as soon as possible but no later than 5 working

847 days after the Sponsor makes this determination and no later than 15 working days after first receipt  
848 notice of the UADE.

849 The investigators are also required to report, without unjustified delay, all device deficiencies that could  
850 have led to a UADE, including device deficiencies, irrespective of whether an adverse event occurred.

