888 device use for safety reasons (e.g. product recall). The affected study activities may resume if the  
889 underlying problem can be corrected by a protocol or system modification that will not invalidate the  
890 results obtained prior to suspension.

891 In addition to the suspension of closed-loop mode use due to a UADE as described above, closed-loop  
892 system use will be suspended for a root cause analysis if there are 5 or more cases of severe  
893 hypoglycemia or five or more cases of hyperglycemia/ketotic events qualifying as SAEs across the entire  
894 study in participants who have initiated Control-IQ technology use.

895 For pediatric participants, the study will be suspended for that cohort for a root cause analysis if there are  
896 3 or more cases of severe hypoglycemia or 3 or more cases of hyperglycemia/ketotic events qualifying as  
897 SAEs across the pediatric participants who have initiated Control-IQ technology use.

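### Events that count toward the 6.6.2 pause rule whatever their cause get a 24-hour report only if the site judges them possibly related, so some may be reported up to 7 days after site awareness

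*Protocol*

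**What the plan says.** **Pause rule (Protocol 6.6.2).** Closed-loop "system use will be suspended for a root cause analysis if there are 5 or more cases of severe" hypoglycemia, or at five or more hyperglycemic/ketotic events that qualify as SAEs, across the study. The pediatric cohort is suspended at 3 or more of either type. Neither threshold mentions relationship to device or drug.

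**Single-event review (Protocol 6.6.1).** The Medical Monitor and the Sponsor review each DKA and each severe hypoglycemia event for cause.

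**Reporting clocks (Protocol 6.4).** The expedited class is "SAEs possibly related to a study device, study drug, or study participation and UADEs and SUSARs". These "must be reported by the investigator to the Coordinating Center within 24 hours of the site becoming" aware. The remaining "reportable ADEs and other reportable AEs should be submitted by completion on the on line form" within 7 days of site awareness.

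**Seriousness and presumption (Protocol 6.2.3 and 6.2.4).** Severe hypoglycemia and DKA are to be treated as SAEs for reporting. Section 6.2.3 adds that when a severe hypoglycemia event "occurs during use of a study device, it generally will be considered to be unrelated to the device (per" section 6.2.6), on condition that the device worked as intended and shows no apparent flaw in its intended function. Section 6.2.4 says the same for hyperglycemia/DKA.

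**Medical Monitor review (Protocol 6.5).** SAEs are typically reviewed within 24 hours of being reported.

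**The concern.** The pause rule and the reporting rule define their events differently. The pause rule counts events without asking why they happened. The reporting rule asks first whether the event may be related, and expedites it only if so. Making severe hypoglycemia and DKA serious for reporting purposes does not close the gap, because 6.4 expedites possibly related SAEs, not all SAEs.

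An event can therefore count toward a study-wide or pediatric suspension while sitting on the slow clock. Until it is reported, those who apply the rule are working from a count that is too low, and the Medical Monitor and Sponsor cannot begin the single-event review that 6.6.1 requires. The participants exposed meanwhile include children, whose threshold is the lower one.

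**Working it through.** The documents give no figure for this point, so there is none to reproduce. The check is a comparison of rules plus clock arithmetic.

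**1. Which clock applies to a counted event (6.4)**

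| Site's judgement of the event | Counts under 6.6.2? | Time allowed from site awareness to report |
|---|---|---|
| Possibly related (or stronger) to device, drug or participation | Yes | 24 hours |
| UADE or SUSAR | Yes, if severe hypoglycemia or a hyperglycemic/ketotic SAE | 24 hours |
| Unrelated or unlikely related to all three | Yes | 7 days |

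Only the last row is a problem. No section moves it to 24 hours.

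**2. Longest permitted time from site awareness to Medical Monitor review (6.4 plus 6.5)**

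- Possibly related: 24 h + 24 h = 48 h.
- Judged unrelated: 7 × 24 h + 24 h = 192 h.
- Difference: 192 − 48 = 144 h, or 6 days, all from the reporting clock.

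Section 6.5 describes the 24-hour review as typical, not as a limit, so both totals are approximate.

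**3. Effect on the pause**

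The rule can act when the 5th (pediatric: 3rd) counted event is known. If each report is delayed by at most 6 extra days, the date on which the threshold is known to be reached also moves by at most 6 days. It moves only if a delayed report is needed to complete the count.

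**4. Could another event occur while a report is pending? (illustration only)**

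Assumptions:
- All participants are on treatment at once, which overstates exposure because enrollment is staged.
- 100 pediatric participants (80 aged 6–13 plus 20 aged 14–17) and 60 to 100 adults.
- Poisson counts at the 3-month severe hypoglycemia proportions in SAP Table 1, spread over 13 weeks.

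Inputs from Table 1:
- CGM users: pediatric (14+15)/(414+584) = 2.91%; adult (17+36+39)/(424+684+577) = 5.46%.
- Overall rows: pediatric (62+155)/(1313+3183) = 4.83%; adult (138+157+189)/(2445+2143+1976) = 7.37%.

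Formula: P(at least one in 7 days) = 1 − exp(−E/13), and in 1 day 1 − exp(−E/91), where E is the expected number over 13 weeks.

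| Case | E | P in 7 days | P in 1 day |
|---|---|---|---|
| CGM-user rows, 100 + 60 | 6.18 | 37.8% | 6.6% |
| Overall rows, 100 + 100 | 12.20 | 60.9% | 12.5% |
| Pediatric only, CGM-user rows | 2.91 | 20.0% | – |
| Pediatric only, overall rows | 4.83 | 31.0% | – |
| If E is only 1 | 1 | 7.4% | 1.1% |
| If E is only 4 | 4 | 26.5% | 4.3% |

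These are chances that some new event occurs in the window, not that a pause is delayed. Table 1 is a registry population and required seizure or loss of consciousness, which is narrower than the trial's definition. The finding does not depend on these figures.

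**The case against.** The strongest objection is that the 7-day route is narrow. The presumption in 6.2.3 and 6.2.4 concerns the device alone, is softened by the word generally, and lapses if the device malfunctioned. Section 6.4 also expedites events possibly related to the drug or to participation. The study drug is an insulin, and 1.3.1.8 lists hypoglycemia first among its potential reactions. The bar in 6.2.6 is low: possibly related needs only reasonable timing and a weak scientific basis, whereas unlikely related requires that the timing not fit. Much severe hypoglycemia on study insulin would meet that bar and go on the 24-hour clock.

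This stands, and it limits the point. What remains is any counted event that the site attributes wholly to something else, for example a ketotic SAE put down to an underlying illness. How often that happens depends on how each site reads the relatedness scale, and the timing of a pause rule should not depend on that.

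Four stronger readings are tempting, but the documents do not support them:

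- **That these events are routinely reported a week late.** The text permits 7 days only when the site rules out device, drug and participation.
- **That the Medical Monitor must approve continued device use after a single event.** Under 6.6.1 the requirement is the site investigator's belief that recurrence is unlikely and use is safe. The Medical Monitor holds an additional power to discontinue. The site's safeguard does not wait for the report.
- **That the reporting rule is circular because 6.2.6 says "Reporting requirements will be based on the Medical Monitor's assessment".** That section closes by defining related events for IRB and FDA reporting, so the sentence reads naturally as governing onward reporting, not the site's first notice.
- **That sites may go weeks without asking about these events.** The synopsis says "Weekly phone/email/text contacts will be performed as part of the comprehensive plan to monitor for adverse events, to include infusion site reactions", while 3.1.4 describes the contact by infusion-site issues: "Participants will receive a weekly contact (phone, email and/or text message) to assess any issues related" to the current site. But 3.1.4 does not say that nothing else is asked, and the synopsis requires adverse event assessment at all visits and contacts. Section 5.1 adds contacts around each challenge, and 3.1.1 asks participants to call about any health-related issue. The two descriptions are at most a minor wording point to reconcile.

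**Conclusion.** The point holds in a limited form. Section 6.6.2 counts events regardless of cause, while 6.4 expedites them only if they are possibly related. A counted event judged unrelated to device, drug and participation may be reported up to 7 days after site awareness, 6 days later than a related one, with Medical Monitor review at about 192 hours instead of about 48. Any resulting delay in knowing that a threshold has been reached is bounded by the same 6 days.

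This rests on two assumptions: that sites use the full time allowed, and that the review takes its typical 24 hours. Time before the site learns of the event is separate and is not part of this finding. The documents do not show how many counted events would fall on the slow clock, and it may be few. Thresholds of 5 and 3 are low enough that one such report can matter, and the remedy is cheap, so the change is worth making.

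**What to change.** In Protocol 6.4, add to the 24-hour class every severe hypoglycemia event, every DKA and every hyperglycemic/ketotic SAE counted under 6.6.2, to be reported to the Coordinating Center within 24 hours of site awareness regardless of relationship. The relatedness assessment can follow, and the definitions, thresholds and causality guidance stay as they are. The longest time from awareness to report for these events falls from 7 days to 1, and to Medical Monitor review from about 192 to about 48 hours.

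The cost is one wording change and faster paperwork for a small number of events. When the protocol is next edited, the descriptions of the weekly contact in the synopsis and 3.1.4 can be brought into line.

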## 851 **6.5 Safety Oversight**

852 The study Medical Monitor will review all adverse events and adverse device events that are reported  
853 during the study and assess the relationship to the study device/drug. SAEs typically will be reviewed  
854 within 24 hours of reporting. Other AEs typically will be reviewed on a weekly basis. Additionally, the  
855 Medical Monitor will review compiled safety data at periodic intervals.

856 The Sponsor will be informed of all reported adverse events and the Medical Monitor's assessment of  
857 relationship to the study device/drug; and informed of all reported device issues.

## 858 **6.6 Stopping Criteria**

### 859 **6.6.1 Participant Discontinuation of Study Device**

860 In the case of an unanticipated system malfunction resulting in a severe hypoglycemia or DKA event  
861 (or a malfunction that could have led to severe hypoglycemia or DKA), use of the study device will be  
862 suspended while the problem is diagnosed. The UADE will be reported to the IRB and FDA. After  
863 assessment of the problem and any correction, use of the study device will not be restarted until approval  
864 is received from the IRB and FDA.

865 In the absence of a device malfunction, use of the study device by a participant will be discontinued if  
866 any of the following occur:

- 867 • The investigator believes it is unsafe for the participant to continue on the intervention.  
868 This could be due to the development of a new medical condition or worsening of an existing  
869 condition; or participant behavior contrary to the indications for use of the device that imposes  
870 on the participant's safety
- 871 • The participant requests that the treatment be stopped
- 872 • Participant pregnancy
- 873 • Two distinct episodes of DKA as defined in section 6.2.3
- 874 • Two distinct severe hypoglycemia events as defined in section 6.2.3
- 875 • One episode of DKA as defined in section 6.2.4 and one severe hypoglycemia event as defined in  
876 section 6.2.3

877 Each DKA, severe hypoglycemia event, or significant infusion site reaction will be reviewed by the  
878 Medical Monitor and by the Sponsor with respect to determination of cause and whether the occurrence  
879 of the event can be attributed to use of the study device or study drug.

880 An additional requirement for continued study device use following a single DKA or severe  
881 hypoglycemia event will be that the site investigator believes that the event is unlikely to recur and that  
882 it is safe for the participant to continue to use the system. Additionally, if the Medical Monitor determines  
883 that the occurrence of the event indicates that it is not safe for the participant to continue to use the study  
884 device, use will be discontinued.

885 **6.6.2 Criteria for Suspending or Stopping Overall Study**

886 In addition to the suspension of device use due to a UADE as described in section 6.2.1, study activities  
887 could be similarly suspended if the manufacturer of any constituent study device requires stoppage of  
888 device use for safety reasons (e.g. product recall). The affected study activities may resume if the  
889 underlying problem can be corrected by a protocol or system modification that will not invalidate the  
890 results obtained prior to suspension.

891 In addition to the suspension of closed-loop mode use due to a UADE as described above, closed-loop  
892 system use will be suspended for a root cause analysis if there are 5 or more cases of severe  
893 hypoglycemia or five or more cases of hyperglycemia/ketotic events qualifying as SAEs across the entire  
894 study in participants who have initiated Control-IQ technology use.

895 For pediatric participants, the study will be suspended for that cohort for a root cause analysis if there are  
896 3 or more cases of severe hypoglycemia or 3 or more cases of hyperglycemia/ketotic events qualifying as  
897 SAEs across the pediatric participants who have initiated Control-IQ technology use.

